### **Study Design Type**

This will be a prospective observational study with pre-specified Aims and Hypotheses. Oscillometry will be performed in term and preterm infants with and without lung disease. Our study will analyze lung function measures obtained in conjunction with routine clinical care in the NICU, as well as normative comparison data obtained from healthy full-term infants in the well-baby nursery. Both cross-sectional (term vs preterm; BPD vs non-BPD) and longitudinal comparisons (disease progression and therapeutic response) will be performed.

### **Eligibility Criteria**

Infants in the UAB NICU or well-baby nursery will be eligible for enrollment. NICU participants must be off ventilator/CPAP support for  $\geq 12$  hours to be included in this study. Term and preterm infants without lung disease will provide comparative normative data on respiratory mechanics during the neonatal period. Disease cohorts will include BPD, RDS, TTN, and MAS as common respiratory disease represented in a NICU population. Clinical benefit of physician-directed treatments will assess response to systemic steroids, inhaled steroids, and diuretics.

### **Study Intervention/Methods**

Serial non-invasive oscillometry at scheduled intervals.

### **Outcomes**

Measures of Pulmonary function quantified by oscillometry will be 1) airway resistance, 2) lung compliance, 3) reactance, 4) and inertance, in newborn infants with and without lung disease (RDS, BPD, TTN, and MAS). All measures will be obtained with the same oscillometry measure.

## **SECTION 2. CONFLICT OF INTEREST DISCLOSURES**

---

### **Financial Conflicts of Interest of the Institutions and Investigators**

[name] and co-investigators have no financial relationships to disclose or conflicts of interest to resolve.

### **Plan for Managing Identified FCOIs**

None needed.

## **SECTION 3. STATEMENT OF PROBLEM**

---

### **3.1. PRIMARY AIM OR QUESTION**

Oscillometry is a feasible tool to detect clinically meaningful changes in lung function in term and preterm infants and distinguish respiratory health from disease.

### **3.2. SECONDARY HYPOTHESIS OR QUESTIONS (S) (IF APPLICABLE)**

- 1) Oscillometry can detect disease progression (e.g., BPD, RDS, TTN and MAS) and resolution in infants hospitalized in the UAB NICU.
- 2) Oscillometry can inform therapeutic response to common pulmonary interventions (e.g., systemic steroids, inhaled steroids, and diuretics) in infants hospitalized in the UAB NICU.
- 3) To determine how pulmonary function differs over time between preterm infants with RDS which resolves and preterm infants with RDS who go on to develop BPD.
- 4) To determine the effects on pulmonary function measurements of medications and treatments given to newborn infants to treat bronchopulmonary dysplasia including physical therapy, methylxanthines, furosemide, chlorothiazide, inhaled and systemic corticosteroids, cromolyn sodium, and albuterol.

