#### **4.2.4. Control or Monitoring of Co-interventions**

Aim 1 control: baseline oscillometry measurements will be compared over time between preterm infants and term infants without lung disease as defined by need for respiratory support.

Aim 2 control: preterm infants with RDS who go on to develop BPD will be compared with preterm infants with RDS who do not go on to develop BPD. Preterm infants who do not develop BPD will serve as controls for RDS infants who develop BPD.

Aim 3 control: baseline pulmonary function tests and serial changes over time will be compared between infants with and without lung disease. Preterm infants without lung disease will act as controls for preterm infants with lung disease. Term infants without lung disease will act as controls for term infants with lung disease.

Aim 4 control: The timing of pulmonary function testing among infants with lung disease will be recorded in relation to the timing of interventions, as ordered by the treating physician, which may affect pulmonary function including bronchodilators, steroids, diuretics, methylxanthines, different forms of physical therapy, and nebulized/inhaled medications, to determine the effects of these treatments on pulmonary function pairing the pre-treatment pulmonary function values (control) for an individual patient with the post-treatment values (intervention) for the same individual patient.

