#### **4.2.5. Primary Outcome**

The primary outcome will be change in lung reactance at 7 Hz ( $X_7$ ) quantified by oscillometry in each comparison group.

In Aim 1, we will compare lung function between term and preterm infants without lung disease at baseline, 24 hours, 48 hours, 72 hours, 7 days, and weekly thereafter until discharge.

In Aim 2, we will compare lung function between preterm infants with RDS who develop BPD and those who do not develop BPD.

In Aim 3, we will longitudinally evaluate change in lung function in NICU patients with lung disease (BPD, RDS, TTN, MAS) at diagnosis, 24 hours, 48 hours, 72 hours, 7 days, and weekly thereafter until resolution of disease state or NICU discharge.

In Aim 4, we will longitudinally evaluate lung function response to therapeutic intervention.

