### 5.1. STATISTICAL ANALYSIS PLAN

Results will be analyzed by the Student's t test, as appropriate for parametric data, and by Mann-Whitney U rank sum test for nonparametric data. A  $p$  value of  $<0.05$  will be considered statistically significant.

Non-independent parametric data will be analyzed by the paired Student's t test, and Wilcoxon signed rank test for non-independent non-parametric data.

Chi-square or Fisher's exact test will be used as appropriate to analyze categorical data.

Analysis of covariance and multiple regression models will be used to examine the interaction between, and the independent effects of factors including birth weight, gestational age, gender, ethnicity, socioeconomic group, maternal smoking, type and severity of lung disease, treatment with surfactant (including number of doses), days of mechanical ventilation before study entry, days of respiratory support before study entry, treatment with antenatal steroids, and treatment with postnatal steroids upon primary and secondary outcomes.

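### Outside the RDS-to-BPD comparison, no planned analysis relates within-infant X7 change to clinical worsening or recovery, so Section 3.2 item 1 (progression and resolution) is not directly tested

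*Combined protocol and SAP*

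**What the plan says.** The hypothesis in Section 3.2 item 1 is that "Oscillometry can detect disease progression (e.g., BPD, RDS, TTN and MAS) and resolution in infants hospitalized in the UAB NICU". Item 3 of the same section asks a narrower question, about "preterm infants with RDS which resolves and preterm infants with RDS who go on to develop BPD".

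Section 4.2.5 makes the primary outcome change in X7, "quantified by oscillometry in each comparison group". For Aim 3 it reads "In Aim 3, we will longitudinally evaluate change in lung function in NICU patients with lung disease (BPD, RDS, TTN, MAS) at diagnosis", followed by later time points and then "weekly thereafter until resolution of disease state or NICU discharge". Resolution therefore enters Aim 3 as the end of measurement, not as an analysis variable.

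Section 4.2.4 gives the Aim 3 comparison: "baseline pulmonary function tests and serial changes over time will be compared between infants with and without lung disease", with preterm controls for preterm infants and term controls for term infants.

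Section 5.1 lists tests by type of data. For repeated data it says "Non-independent parametric data will be analyzed by the paired Student's t test", with the signed rank test as the non-parametric alternative. It also names analysis of covariance and multiple regression, with type and severity of lung disease among the factors. The timing of the severity rating is not stated.

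Section 5.2 sizes Aim 3 on initial X7 values, diseased against control.

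**The concern.** A claim that a measurement detects progression and resolution needs two things: a definition of those states that does not depend on the measurement, and an analysis of whether the measurement moves with them. For item 1 the plan supplies neither, except that RDS infants are split by whether they later develop BPD.

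The plan's own assumptions put the two courses in opposite directions. Section 5.2 takes disease as a more negative X7 (Aim 3) and expects a more positive X7 after most of the treatments in Aim 4. If a diagnosis contains both worsening and recovering infants, a change summarised over the whole diagnosis nets one against the other.

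Two misreadings are then possible. A small group change could be taken as failure to detect change, although X7 had followed individual infants well. A clear group change could be taken as proof that X7 tracks disease, although it shows only that the diagnosis group changed differently from controls.

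**Working it through.** **The plan's own figure.** Section 5.2, Aim 3 (RDS, BPD, TTN): difference 0.20 of the mean, SD 0.5, power 90%, type I error 5%. Sidedness is not stated; two-sided is used here.

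n per arm = 2 × (1.960 + 1.282)² × 0.5² / 0.20² = 131.3, rounded up to 132, so 264 in total. This matches. For MAS, with difference 0.50, the same formula gives 21.01, which rounds up to 22 per arm (44 in total) against the stated 21 (42), a trivial gap. Both figures size a contrast of initial values. No figure in Section 5.2 sizes an Aim 3 analysis of change.

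**Where clinical course appears in the plan**

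| Place | Split by course? |
|---|---|
| 3.2 item 3; Aim 2 in 4.2.4 and 5.2 | Yes, RDS only, one eventual label per infant (BPD or not) |
| Aim 3 in 4.2.4 | No: diseased against not diseased |
| Aim 3 in 4.2.5 | No: by diagnosis; resolution ends follow-up |
| 5.1 | Severity is a listed factor; change in status between tests is not |

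TTN, MAS and established BPD, all named in item 1, have no analysis by course.

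**Illustration of offsetting.** These inputs are assumptions, apart from the 132 and the 20%, which are borrowed from Section 5.2, where they describe initial values. There are 132 diseased infants; a share w changes by −0.20 of the mean and the rest by +0.20. The SD of change s within each course is 0.5, ranged from 0.35 to 0.7.

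- Mean change = 0.20 × (1 − 2w)
- Variance of change = s² + 0.16 × w(1 − w)
- Noncentrality = mean / (SD of change / √132), two-sided paired t test, 131 degrees of freedom

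Worked case, w = 0.25 and s = 0.5: mean 0.10; variance 0.25 + 0.16 × 0.1875 = 0.28; SD 0.529; noncentrality 0.10 / (0.529 / 11.49) = 2.17; power 58%.

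For comparison, the same 132 infants can be split by course: difference 0.40, SD s, two-sample t test. Both columns show s = 0.5, with the range for s from 0.7 to 0.35 in brackets.

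| Share worsening | Whole cohort, paired | Worsened against improved |
|---|---|---|
| 10% | 94% (73% to >99%) | 78% (50% to 97%) |
| 25% | 58% (35% to 83%) | 98% (81% to >99%) |
| 50% | 5% (mean change is 0) | >99% (90% to >99%) |

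The split column assumes that every infant changes and is classified correctly. If half the infants are unchanged and the rest keep the 25% mix, about 66 contribute (49.5 against 16.5) and the split contrast has 79% power at s = 0.5. The whole-cohort test then has mean 0.05, variance 0.25 + 0.5 × 0.04 − 0.05² = 0.2675, noncentrality 1.11, and power of about 20%.

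**The case against.** The best defence is that the plan does use clinical course. Aim 2 and item 3 compare RDS that resolves with RDS that becomes BPD, sized at 132 against 132. This stands for RDS, and it is why the point is limited to what lies outside that comparison. It does not cover the other three diagnoses, and an eventual label is not the same as worsening or improvement between two tests.

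A reader might infer that the plan averages worsening and recovering infants so that their changes cancel. The documents do not say so. Section 5.1 assigns no test to Aim 3, and a whole-diagnosis change is only the natural result of following the comparison that is stated. Nor does the 132 against 132 in Aim 2 imply a half-and-half mix: RDS enrolment is open-ended until the BPD target is met, and later BPD is not the same as a worsening X7. The 5% row is therefore an extreme case, not a forecast.

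A reader might also infer that the planned result answers neither half of item 1. That is too strong. Comparison with term or preterm controls partly deals with maturation. Where nearly all infants recover, change from diagnosis to resolution is informative about resolution, and at 10% worsening the whole-cohort test is the more powerful of the two (94% against 78%).

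Finally, infants enter after at least 12 hours off ventilator or CPAP (Section 4.1.1), so support level may vary little between tests. That stands as a practical limit on the remedy.

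**Conclusion.** The point holds as a gap in the analysis of one secondary hypothesis. For TTN, MAS and established BPD the plan neither defines progression or resolution nor relates within-infant X7 change to them. For RDS it does so only through eventual BPD status. The Aim 3 result as planned can show that X7 changes differently in diseased infants and controls; it cannot show that X7 follows clinical course.

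This conclusion rests on the text and needs no power calculation. How much opposite changes would offset is unknown, because the documents give no share of worsening infants and no SD of change; the 0.5 in Section 5.2 refers to initial values. Under the stated assumptions the loss is small at 10% worsening and large at 25% or more. The sponsor should make the change, but the gap does not undermine the other aims.

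**What to change.** In Section 5.1, for Aim 3:

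1. Record each infant's charted oxygen need or respiratory support at every oscillometry test. The plan already uses both kinds of marker, in Section 5.2 (Aim 2) and Section 4.2.4 (Aim 1).
2. Classify each between-test interval as worsened, unchanged or improved by a rule written in advance and applied without sight of X7.
3. Name as the test of item 1 a longitudinal model of X7 change on that status, by diagnosis, with infant as random effect.
4. Keep the cohort change against controls as a stated analysis beside it, since it is the more powerful of the two where most infants recover.

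The cost is SAP wording and chart extraction at each test date, with no extra tests or infants. Intervals will be wide where a category is sparse, as is likely in MAS (21 per arm) or wherever few infants worsen.

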### **3.3. BACKGROUND AND RATIONALE**

*TremoFlo™* C-100 Airwave Oscillometry System™ (THORASYS Thoracic Medical Systems Inc. Montreal, Quebec, Canada) is a technology for measuring lung mechanics without patient effort. Pulmonary function testing using flow-volume and lung volumes is one of the most widely used tests to objectively measure lung function in adults. Such measurements are dependent on effort and coordination by the patient which is not possible for newborn infants. The minimum age for spirometry is typically 6 years to master the technique ([ATS](#)). Therefore, newborn infants usually require forced exhalation, flow interruption, and often sedation/anesthesia in order to obtain accurate pulmonary function measurements ([Di Fiore](#)). Infant pulmonary function testing can be time-consuming and expensive to perform in newborn infants. This has limited the utilization of this potentially informative method of studying lung function particularly during transition to extra-uterine life, and in newborn lung diseases including RDS, TTN, MAS and BPD and after the effects of treatments given to newborn infants with BPD ([Di Fiore](#)).

The TremoFlo device uses the forced oscillation technique during spontaneous infant breathing and notably does not require any sedation to perform ([Calogero](#)). The forced oscillation technique measures lung function by superimposing a gentle multi-frequency airwave onto the infant's respiratory airflow while the infant breathes spontaneously. Only a short period of breathing is required to obtain a reliable measurement of airway resistance and

reactance (Calogero). Oscillometry has been successfully utilized to quantify lung function in children (Calogero, Duiverman) and adults (Oostveen, Brown) with lung disease, but never previously in newborn infants. This proposal brings this novel technique of measuring lung function to the neonatal population to identify changes in respiratory mechanics between term and pre-term gestations and quantify fluctuations in infant lung function in response to disease progression and therapeutic intervention.

**Oscillometry has detects four measures of lung function:**

**Lung Compliance:** Compliance is a measure of the elasticity or distensibility of the lungs or respiratory system. In neonates, the chest wall is very distensible and in general does not contribute substantially to compliance. It is calculated as follows:

$$\text{Compliance} = \frac{\Delta \text{ Volume (mL)}}{\Delta \text{ Pressure (cm H}_2\text{O)}}$$

Lung compliance has been measured using dynamic and static techniques (Di Fiore). Dynamic lung compliance has traditionally been measured in spontaneously breathing preterm infants using devices to measure tidal volume and esophageal pressure. The difference between end-inspiration and end-expiration serve as quasi static points of reference. However, in infants with high respiratory rates such as newborn infants and those with lung disease this technique may underestimate the true compliance. Static lung compliance is calculated between points of no flow when the respiratory muscles are relaxed by occluding the airway to allow for equilibration of pressure throughout the respiratory system. Compliance is then calculated by dividing the total exhaled volume by the pressure change during the occlusion minus the pressure at end expiration. One advantage of this technique is that it does not require esophageal pressure monitoring. However, this technique allows a single measurement of compliance to be made only. The single-interruption technique has been modified using the multiple-interruption technique during expiration. The multiple measurements obtained can demonstrate changes in compliance within a single breath as the lungs fill.

**Airway Resistance:** Conversely, infants with increased resistance of the respiratory system, such as those with broncopulmonary dysplasia, may compensate by using slower and larger breaths ([name]). Resistance is a measure of the ability of the gas conducting part of the respiratory system and lung tissue to impede flow and includes airway resistance (the nasopharynx, larynx, trachea, and bronchi) and viscous resistance (tissue moving against tissue). Resistance is calculated as follows:

$$\text{Resistance} = \frac{\Delta \text{ Pressure (cm H}_2\text{O)}}{\Delta \text{ Flow (L/sec)}}$$

Usually the mid-volume point of the breath is used for the calculation above. Similar to compliance, measurements using the interruption and multiple-interruption techniques allow for resistance to be measured, the latter at different points during the respiratory cycle (Di

[Fiore](#)). With multiple-interruption the pressure at the point of occlusion is divided by the flow immediately preceding the occlusion. Multiple-interruption techniques allow the components of resistance from the airway and tissue to be separated out. In spontaneously breathing infants with lung disease the flow in the airways may be turbulent causing the resistance to change during the respiratory cycle. The forced oscillation technique superimposes oscillatory waves of different frequencies throughout the respiratory cycle to determine both the overall respiratory system resistance as well as changes in central and heterogeneous resistance [\(ATS\)](#).

**Reactance:** Reactance is a measure of the energy conservation in the respiratory system and includes elastic fibers in the lung tissue which determine lung compliance and the inertive forces of acceleration and deceleration of the column of air in both the airway tree and lung tissues. Resistance is a measure of the ability of the gas conducting part of the respiratory system and lung tissue to impede air flow. This includes airway resistance (through the nasopharynx, larynx, trachea, and bronchi) and viscous resistance (tissue moving against tissue). Resistance and reactance of the lung tissues are affected in different patterns depending on the location and the type of lung disease. For example, central obstruction increases resistance without changing reactance. Homogenous peripheral obstruction increases resistance and decreases reactance. Heterogenous peripheral obstruction similarly increases resistance and decreases reactance; however, the increase in resistance is larger at higher frequency oscillations compared with lower frequency oscillations. Therefore, the forced oscillation technique may allow determination of the presence, type, severity, and location of lung disease in infants.

**Inertance:** Inertance is a measure of the tendency of the respiratory system to resist changes in flow. In healthy adults and children inertance is a minor component of the forces in the respiratory system. However, inertance increases with increasing respiratory rate as is commonly seen in newborn infants. The equation of motion defines the relationship between pressure, flow, volume, and the elastic, resistive, and inertial components of the respiratory system. It is calculated as follows where P is the pressure that produces lung inflation, C is the compliance, V is the volume, R is the resistance,  $\dot{V}$  is flow, I is inertance, and  $\ddot{V}$  is acceleration:

$$P = \frac{V + R\dot{V} + I\ddot{V}}{C}$$

While the respiratory system is often modeled as being composed of a single constant compliance and a single constant resistance, the mechanical properties vary with changes in the lung volume, even within a breath between inspiration and expiration. In addition, lung disease (such as bronchopulmonary dysplasia) can be heterogeneous, and thus, different areas of the lungs can have varying mechanical characteristics. The forced oscillation technique will allow us to differentiate between different patterns of resistance and compliance/inertance within each breath to better understand lung mechanics in both healthy newborn infants and infants with the pre-specified types of lung disease (RDS, BPD, MAS, and TTN). The forced oscillation technique may also be useful for measuring the effectiveness of interventions given to treat or prevent lung disease including bronchopulmonary dysplasia.

The respiratory rate is highest at birth and decreases through infancy and early childhood (Fleming). Several physiological reasons have been proposed to explain this difference including differences in pulmonary and chest wall compliance and resistance (Kerem). Faster respiratory rates and lower tidal volumes may be optimum in spontaneously breathing preterm and term infants on the first day after birth to decrease the work of breathing. Compared to term infants, preterm infants have markedly decreased lung compliance (0.1-1.0 mL/cm H2O/kg versus 3-5 mL/cm H2O/kg) and somewhat decreased resistance (22 H2O/L/second versus 29 cm H2O/L/second) (Avery, Di Fiore). The higher spontaneous respiratory rate of preterm infants when compared with term infants is likely due to their lower lung compliance as increasing the respiratory rate rather than the tidal volume requires less work. Minute ventilation is a product of tidal volume and respiratory rate.

The spontaneous respiratory rate for any given minute ventilation is governed by the principle of minimal work. During spontaneous breathing, the respiratory muscles must work to overcome the elastic and resistive forces of the chest wall and lungs that decreases the pulmonary system compliance (Otis). When the spontaneous respiratory rate is low, excessive work has to be generated by the respiratory muscles to overcome lung and chest wall elastic forces in order to achieve larger tidal volumes. The spontaneous respiratory rate in a cohort of 24 preterm infants during temporary disconnection from ventilators ranged from 53-114 breaths per minute (Greenough). There was a significant negative correlation between gestational age and spontaneous breathing rate ( $r = 0.85$ ). This observation is supported from well-known animal data which show that smaller animals breathe faster than larger animals (Widdicombe). Therefore, more efficient alveolar ventilation can be achieved by increasing the respiratory rate rather than increasing the tidal volume (Davis).

**Conclusion:** Previous evaluation of lung function in term and preterm neonates has been limited, lessening detection of disease onset, progression, and therapeutic response. The ease of oscillometry that only requires tidal breathing eliminates the need for patient cooperation and maneuvers that previously excluded lung function testing in the NICU. This proposal will evaluate the feasibility and clinical value of oscillometry in newborns, both to detect changes in premature compared to full-term gestations as well as disease cohorts. The four Specific Aims proposed in this study offer significant potential to bring this novel measure of lung function to neonatal care and introduce functional measures of lung function to bedside care.

